#### **Criteria for Removal from Study**

Progressive or resistant disease (defined as CSF with persisting blasts after four intra-lumbar administrations of rituximab, which is after 2 weeks of therapy)

Unacceptable severe (grade 3-4) toxicity that is possibly related to the study drug and persists despite dose optimization and optimal management of toxicity.

Patient choice

Failure to comply with study schedule

### **Statistical Considerations**

The primary outcome of the study will be response rate. Time to recurrence of CNS leukemia and overall survival will be secondary outcomes. Time to recurrence and survival will be considered from the date of CNS relapse diagnosis.

There is no well-defined metric to measure response to treatment in patients with peripheral nerve involvement only. Clinical and radiologic response will be recorded and it is expected that few to no patients with only peripheral nerve involvement will actually be involved and therefore the statistical analysis will not be affected.

A maximum of 25 patients will be enrolled in this phase I/II study, with about 12 patients/year.

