### **Inclusion Criteria**

Patients must have relapsed or refractory CD20+ lymphoid malignancies with either documented CNS involvement or peripheral nerve infiltration.

Patients 3 years of age and older are eligible after 3 patients (age 15 or older) have been treated and did not experience a dose limiting toxicity. Patient 3 to 15 years of age will follow the dose escalation schema independent of the adults.

ECOG performance status measure will be used. (ECOG Performance Status less than or equal to 3)

Adequate liver function (bilirubin less than or equal to 3 mg/dL within 24 hours of enrollment)

Adequate renal function (serum creatinine less than or equal to 3 mg/dL within 24 hours of enrollment)

Urine pregnancy test for women of childbearing potential (defined as *not* post-menopausal for 12 consecutive months or no previous surgical sterilizations). A negative urine pregnancy test is required within 48 hours of initiating study drug.

Signed informed consent

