#### Selection of Patients:

Patients will be eligible for the study if they relapsed and/or refractory CD20+ lymphoid malignancies (all patients beyond complete remission 1 are considered eligible). Upon suspicion of LMD, the patients will be screened for the protocol. The preference at this point will be for the patient to receive a diagnostic lumbar puncture (i.e., no chemotherapy administered). However, if it is deemed necessary to instill conventional chemotherapy (e.g., methotrexate or cytarabine) during the first lumbar puncture, these patients will still be eligible for the protocol. The two groups will be analyzed separately for all outcomes (i.e., patients who received no intrathecal chemotherapy prior to receiving intrathecal rituximab, and patients who received cytarabine or methotrexate before commencing intrathecal rituximab). If a patient had received IT methotrexate or cytarabine and is subsequently enrolled, at least 48 hours should elapse from the administration of methotrexate or cytarabine to the first application of IT rituximab.

Once enrolled, the patients will go on to receive rituximab 10 mg intrathecally twice weekly until 2 consecutive CSF samples are negative for the presence of blast cells 48 hours must elapse between intrathecal rituximab doses. Thereafter, rituximab 10 mg intrathecally will be administered weekly for an additional 4 weeks, followed by intrathecal rituximab 10 mg administered once every other week for an additional 8 weeks.

After the first three patients are enrolled and followed for at least 2 weeks, if no dose limiting toxicity is experienced, all subsequent patients will be given rituximab 25 mg intrathecally on an identical schedule as described above. This dose was identified as the maximum tolerated dose in the phase I study

conducted by Rubenstein and colleagues. If excessive toxicity is noted in the first 3 patients given rituximab 25 mg (with at least two weeks of follow up), we will move back to the 10 mg dose, and that will be the final dose employed going forward.

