### **Analysis method**

Data analysis will be performed using SAS or S-plus, as appropriate. All patients who received at least 1 dose of the agent will be included in the intent-to-treat analysis for efficacy. Demographic and disease characteristics of the patients at registration will be summarized using descriptive statistics such as mean, standard deviation (SD), median and range. Overall response rates will be presented with 95% confidence intervals. The association between response and patient and disease characteristics will be examined by two-sample t-test or Chi-square test.

The data from all patients who received the therapy during the study will be included for safety analysis. Safety data will include laboratory, physical exam, and adverse event reports on study patients. These descriptive summaries will be provided for all patients for each safety parameter by intrathecal rituximab dose #, grade, and relationship to treatment.

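### Overall survival and time to CNS recurrence are counted from CNS relapse diagnosis, but only dosed patients are analysed, so both clocks include time in which the event cannot be counted

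*Protocol*

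**What the plan says.** Protocol, Statistical Considerations, makes time to CNS recurrence and OS the secondary outcomes and sets their origin: "Time to recurrence and survival will be considered from the date of CNS relapse diagnosis". The SAP repeats this under the same heading.

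Protocol, Analysis method, defines who is analysed: "All patients who received at least 1 dose of the agent will be included in the intent-to-treat analysis for efficacy".

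Protocol, Selection of Patients, describes the order of events. "Upon suspicion of LMD, the patients will be screened for the protocol", and "The preference at this point will be for the patient to receive a diagnostic lumbar puncture", without chemotherapy. If intrathecal chemotherapy is given at that puncture, "at least 48 hours should elapse from the administration of methotrexate or cytarabine to the first application of IT rituximab". No maximum interval from diagnosis to first dose is stated there or in the Inclusion Criteria.

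Criteria for Response judges response on the CSF after four rituximab punctures. Criteria for Removal from Study places four administrations at 2 weeks of therapy.

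The Protocol provides no delayed entry, no landmark, and no rule for the recurrence time of patients whose CSF never clears. Its Analysis method section names no time-to-event method. The SAP text available ends within the Efficacy section, so these absences can be checked only in the Protocol.

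**The concern.** A patient enters the efficacy set on the day of the first dose, but the clock started earlier, at diagnosis. Anyone who died in between is not in the set. For those who are, that interval is guaranteed survival, and the plan adds it to their OS.

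The recurrence clock has a second problem. A recurrence can be counted only after the CNS disease has cleared, yet the clock starts when disease is present. A responder is credited with recurrence-free time while blasts may still be in the CSF. A patient who never clears cannot have a recurrence, and the plan does not say whether that patient is an event, censored or excluded. The analyst would have to choose a rule after seeing the data, so the direction of any error over the whole set cannot be stated.

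At stake is how two secondary outcomes are described. No sample size, stopping boundary or planned formal comparison rests on them.

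**Working it through.** No design figure in the documents depends on this origin, so there is none to reproduce. The schedule is consistent with itself: 4 doses at 2 per week is 2 weeks, as Criteria for Removal from Study states.

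**Inputs**
- Median survival 6 months and one-year survival 28%: the historical series in Protocol, Treatment of Leptomeningeal Disease.
- Sample size: "A maximum of 25 patients will be enrolled in this phase I/II study".
- Minimum of 48 hours between rituximab doses: Selection of Patients.
- Target response rate 25%, historical rate about 10%: Efficacy.
- Diagnosis-to-first-dose interval g: not given. Assumed 2 to 14 days, which at 30.44 days per month is 0.066 to 0.460 months.

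**OS.** Assume exponential survival from first dose with median 6 months and no drug effect, so the rate is ln 2 / 6 = 0.1155 per month. This gives one-year survival of exp(−0.1155 × 12) = 25.0%, near the quoted 28%. Counted from diagnosis, the median is 6 + g and one-year survival is exp(−0.1155 × (12 − g)):

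| g | Median from diagnosis (months) | Added (months) | One-year survival |
|---|---|---|---|
| 0 | 6.00 | 0 | 25.0% |
| 2 days | 6.07 | 0.07 | 25.2% |
| 7 days | 6.23 | 0.23 | 25.7% |
| 14 days | 6.46 | 0.46 | 26.4% |

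**Sampling error.** If all 25 patients have died, the exact exponential 95% interval around a 6-month median is 6 × 50 / χ²(50 df) at the 0.975 and 0.025 quantiles, or 4.20 to 9.27 months. The largest shift in the table, 0.46 months, is small beside it.

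**Recurrence in responders.** From dose 1 to dose 4 takes at least 3 × 2 = 6 days, and the plan puts four doses at about 14 days. If clearance is documented around the fourth dose, the time credited before response is established is:
- g = 2 days: 2 + 6 = 8 to 2 + 14 = 16 days (0.26 to 0.53 months)
- g = 14 days: 14 + 6 = 20 to 14 + 14 = 28 days (0.66 to 0.92 months)

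The CSF may clear before the fourth puncture, so these are upper figures for the blast-positive time.

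**Patients without a defined recurrence time.** Applying the 25% target to 25 dosed patients gives 25 × 0.25 = 6.25 responders and 25 × 0.75 = 18.75 non-responders. At a 10% rate there would be 25 × 0.10 = 2.5 responders.

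**The case against.** The strongest reply is that this is immaterial. The OS shift is a small fraction of the sampling error, no decision depends on it, and the workflow (screening on suspicion, a 48-hour minimum after chemotherapy) suggests an interval of days. All of that stands and sets the severity. It does not answer the recurrence point, which is a missing definition rather than a question of precision.

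A second reply is that diagnosis is a natural origin, and that time since diagnosis is a true description of dosed patients. That is fair, and the plan does not claim to estimate survival of everyone diagnosed. But a dosed-only set counted from diagnosis needs delayed entry before it can be read as a survival curve from diagnosis.

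A reader might infer a larger OS bias. A Weibull curve fitted to the historical 6 months and 28% (shape 0.877, scale 9.11), taken to run from diagnosis, gives a median of 6.72 months in patients who survive a 14-day interval, 0.72 above 6. The clock does not cause all of that. Moving the origin to first dose removes exactly the interval (6.72 − 0.46 = 6.26), and the remaining 0.26 is selection of patients who live long enough to be dosed, which a new origin leaves in place. The historical series also has no stated origin, so the documents do not support it as the truth from diagnosis.

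Two further inferences should not be drawn. One is that the results by prior intrathecal chemotherapy are distorted: the plan says "The two groups will be analyzed separately for all outcomes" but schedules no contrast, and nothing shows that the two groups' intervals differ. The other is that admitting patients "with either documented CNS involvement or peripheral nerve infiltration" undermines the OS clock: Statistical Considerations expects few or no patients with peripheral nerve involvement alone.

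**Conclusion.** The point holds at low severity. As written, OS includes an interval in which no analysed patient can die. Its contribution is 0.07 to 0.46 months if the interval is 2 to 14 days, a range the documents do not supply. In responders, time to recurrence also includes up to about 2 weeks of possibly positive CSF, and for patients who never clear it is undefined. The text establishes the mismatch between origin and analysed set with high confidence. The size is only illustrative, since it rests on the assumed interval and, for the medians and survival percentages, on an exponential curve. Primary endpoint, stopping rules and sample size are unaffected.

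**What to change.** Amend Statistical Considerations in the Protocol and SAP as follows:
- **OS:** measure from the first intrathecal rituximab dose, a date that every patient in the efficacy set has.
- **Time to CNS recurrence:** measure in responders only, from the assessment that establishes response (CSF after four punctures), with death without recurrence as a competing event, and report descriptively. Do not start at an earlier negative sample. A responder must by definition be alive and clear at the four-puncture assessment, so an earlier start would create guaranteed time again.
- **Interval:** report the distribution of time from CNS diagnosis to first dose.

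If a diagnosis-origin OS curve is kept for comparison with history, use delayed entry at first dose and state its limits. With intervals spread evenly over days 2 to 14 and deaths ignored, only 25 × (4 − 2)/12 = 4.2 patients are at risk on day 4 and 25 × (7 − 2)/12 = 10.4 on day 7. Deaths before the earliest entry cannot be recovered.

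The change is one of wording. No case report form is shown, so confirm that the dates of CNS diagnosis, first dose and the response assessment are recorded. The costs are slightly shorter reported times, a recurrence estimate from few patients (about 6 at the 25% target, 2 to 3 at 10%), residual selection of patients who survive to dosing, and possible loss of comparability with a historical series counted from diagnosis.

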### **Phase I**

First, phase I study is performed to assess the safety of two dose levels for rituximab: 10mg and 25mg. These two dose levels have been previously in a small series (12). A 3+3 design will be used to for dose escalation. Detailed dose escalation rules are described in the following section. A maximum of 12 patients will enroll in the phase I study.

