**Title:** Safety and Efficacy of Intrathecal Rituximab in Patients with Lymphoid Malignancies Involving the Central Nervous System

**Primary Investigator:** [name].

**Co-Primary Investigator:** [name].

**Collaborators:** Leukemia Faculty

**Centers:** M. D. Anderson Cancer Center

**Number of Patients:** 25

**Objectives:** to determine the safety and efficacy of intrathecal rituximab in patients with relapsed and/or refractory lymphoid malignancies with involvement of the central nervous system.

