### **Dose Escalation Procedures**

The dose of treatment agent will be escalated in successive cohorts of patients. The starting dose is at dose 0 as shown in table 1. Enroll 3 patients at the dose level and proceed to the next higher dose level with a cohort of 3 patients until at least 1 patient experiences a dose-limiting toxicity (DLT).

DLT is defined as a clinically significant adverse event or abnormal laboratory value assessed as unrelated to disease progression, intercurrent illness, or concomitant medications and meeting the NCI common terminology criteria that are CTCAE Grade 3 or 4.

An adverse event must be clinically significant to define DLT e.g. alopecia, study drug-related fever, electrolyte abnormalities (including K, Na, Cl, HCO3, Mg, Ca) that are < Grade 3 will not define the DLT. Drug-related Grade 3-4 nausea and vomiting not controlled with adequate therapy will be considered DLTs.

If only 1 of 3 patients experiences a DLT at a given dose level, enter 3 additional patients at the current dose level. If only 1 of 6 patients experiences a DLT at a given dose level, proceed to the next higher dose level with a cohort of 3 patients. If at least 2 of 3 or 2 of up to 6 patients experience a DLT at a

given dose level, then the MTD has been exceeded (stopping dose). Once the MTD has been exceeded, treat another 3 patients at the previous dose level if there were only 3 patients treated at that dose level. The MTD is defined as the highest dose level in which 6 patients were treated with at most 1 experiencing a DLT during the 1st cycle.

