In summary, our dose escalation plan is as follows: during phase I, the starting dose is 10 mg and dose escalation will follow a 3 + 3 design. After three patients have received 10 mg, if there is no DLT, the next cohort of three patients will receive 25 mg. If there is one DLT in the initial three patients, an additional three patients will be treated at 10 mg. If 2/6 patients experience a DLT at 10 mg, the study will be closed. If less than or equal to 1/6 at 10 mg experience a DLT, we will enroll the next three patients at 25 mg. The maximum dose on this protocol is 25 mg, thus, no further dose escalation will occur. If 1/3 patients at 25 mg experience a DLT, we will enroll three additional patients at 25 mg. If 2/6 experience a DLT, all subsequent patients will receive 10 mg, and that will be the final dose. If less than or equal to 1/6 experience a DLT at 25 mg, the remainder of the patients enrolled will receive 25 mg. If 2/3 or 2/6 patients experience a DLT at the 10 mg dose, the study will be terminated.

Table 1. Dose levels of rituximab

| Dose level        | rituximab |
|-------------------|-----------|
| 0 (starting dose) | 10 mg     |
| 1                 | 25 mg     |

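### The phase I maximum of 12 counts one dose escalation, but patients aged 3 to 15 have their own, so following the plan can breach it

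*Protocol*

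**What the plan says.** **Two escalations.** Protocol, Inclusion Criteria, makes patients aged 3 and over "eligible after 3 patients (age 15 or older) have been treated and did not experience a dose limiting toxicity", and adds: "Patient 3 to 15 years of age will follow the dose escalation schema independent of the adults".

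**One escalation.** The other sections read as a single sequence:
- Protocol, Phase I (repeated in the SAP): "A maximum of 12 patients will enroll in the phase I study".
- Protocol, Selection of Patients: once the first three patients have been followed without a DLT, "all subsequent patients will be given rituximab 25 mg intrathecally on an identical schedule as described above".
- Protocol, Dose Escalation Procedures, summary paragraph: after at most one DLT in six at the higher level, "the remainder of the patients enrolled will receive 25 mg".
- Protocol, Phase II (repeated in the SAP): one recommended dose, one arm, and a sample size of no more than 22, including the phase I patients treated at the MTD.
- Protocol, toxicity monitoring section: one set of six MTD patients is carried forward.

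**One total.** The synopsis entry "Number of Patients" is 25, and Statistical Considerations says "A maximum of 25 patients will be enrolled in this phase I/II study". The statistical sections do not mention the 3 to 15 age group, a second escalation, or pooling of the age groups.

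**The concern.** A maximum on phase I enrolment should hold on every path the rules allow. Here it was evidently built from one escalation, and a second one draws on the same 25 patients. A team that lets the children escalate separately can pass 12 while obeying every cohort rule. A team that enforces 12 may have to stop one escalation before it is complete.

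The same omission reaches phase II. Every patient treated at a dose that is not carried forward is lost from the 22, and the monitoring tables were run to N = 22. The plan also does not say whether the stopping rules apply to the age groups together or apart, or what happens if the two escalations end at different doses.

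There is a related conflict on dosing. Selection of Patients sends everyone after the first three DLT-free patients to the higher level. That is the point at which Inclusion Criteria admits children to their own escalation, which starts at the lower level. The passages must be reconciled.

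**Working it through.** **Inputs.** Study total 25 (synopsis; Statistical Considerations). Two dose levels, cohorts of 3, expansion to 6 after one DLT in three (Phase I; Dose Escalation Procedures). Phase I patients at the MTD count in phase II (Phase II). Efficacy prior Beta(0.2, 1.8), stop if Pr(response rate > 0.1) < 0.05. Toxicity prior Beta(0.6, 1.4), stop if Pr(toxicity > 0.3) > 0.9.

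**1. Reproduce the plan's figures with one escalation.**
- Phase I maximum: 2 levels × 6 = 12.
- Phase II maximum: 25 − 3 (fewest patients at the non-final dose) = 22.

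Both match the plan.

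**2. Phase I total if both escalations finish.** Full cohorts are assumed, and the opening condition for children is read as 0/3 DLTs in the first adult cohort.
- *Summary paragraph, where 0/3 at the higher level is enough.* Adults: 3 + (3 or 6) = 6 or 9. Children: (3 or 6) + (3 or 6) = 6, 9 or 12. Totals: 12, 15, 18 or 21. Only two escalations without any expansion stay at 12.
- *MTD definition in the same section*, which begins "The MTD is defined as the highest dose level in which 6 patients were treated". Each age group uses 9 or 12. Totals: 18, 21 or 24, so 12 is always exceeded.

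**3. The paediatric escalation need not finish.** Adults 3 + 6 = 9. The fourth child makes 9 + 4 = 13 > 12.

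**4. Phase II ceiling.** Maximum = 25 − all patients, of either age group, treated at the non-final dose. It equals 22 only if no more than 3 are.
- One child at 10 mg, three adults at 10 mg, final dose 25 mg: 25 − 3 − 1 = 21.
- Both finished: 25 − 3 − 3 = 19. If the non-final level expands in one group: 25 − 3 − 6 = 16. If in both: 25 − 6 − 6 = 13; with the 0/3 condition this needs a common final dose of 10 mg.
- For comparison, one escalation alone gives 22, or 25 − 6 = 19 if its non-final level expands.

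**5. Monitoring at N = 22 and N = 19.**

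*Efficacy.* The only reachable stop is 0/9, so P(stop) = (1 − p)^9. At p = 0.05, 0.10, 0.15, 0.20 and 0.25 this is 0.630, 0.387, 0.232, 0.134 and 0.075 (Table 2: 0.63, 0.40, 0.23, 0.14, 0.08). It is the same at N = 22 and N = 19; only the sample-size entries of 22 become 19.

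*Toxicity.* Exact recursion, monitored from patient 6, no stop counted at the last patient:

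| True rate | Table 3 | N = 22, recomputed | N = 19 | N = 19 median (quartiles) |
|---|---|---|---|---|
| 0.2 | 0.05 | 0.050 | 0.048 | 19 (19, 19) |
| 0.3 | 0.22 | 0.228 | 0.209 | 19 (19, 19) |
| 0.4 | 0.54 | 0.539 | 0.491 | 19 (7, 19) |
| 0.5 | 0.82 | 0.824 | 0.773 | 7 (6, 17) |

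The boundaries are the same at each number of patients, so cumulative stopping through patient 18 is identical in the two designs. The difference (0.539 − 0.491 = 0.048 at 0.4; 0.824 − 0.773 = 0.051 at 0.5) comes entirely from stops at patients 19 to 21, which the smaller design does not have.

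**The case against.** Four points can be made for the plan as it stands.

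- *The 22 is a ceiling, and 19, 16 and 13 all respect it.* This stands. One escalation can also end at 19. The phase II figure is therefore a secondary matter.
- *The 12 might refer to the adult escalation only.* Possible, but the sentence speaks of the phase I study as a whole and nothing limits it to adults. If that is the intention, it needs to be written.
- *The conflict depends on children enrolling, and no paediatric accrual is forecast.* True. But a reader might infer that it needs a completed paediatric escalation, so at least six children, and it does not: four are enough after nine adults.
- *The size depends on the reading chosen.* True. The range 12 to 21 needs the summary paragraph and the 0/3 condition. If adults could expand to six at the lower level before children are admitted, 24 is reachable under the summary as well.

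The SAP text repeats the protocol's wording and is no independent evidence.

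Two stronger readings are tempting. One is that the smaller phase II weakens the safety monitoring. It does not: the boundaries at each number of patients are unchanged. The other is that a breach is certain or can be given a probability. Under the summary, two escalations without expansion total exactly 12, and the documents give no DLT rates from which a probability could be worked out.

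**Conclusion.** The firm error is the phase I maximum. It fits one escalation, the plan prescribes two within a shared 25, and the plan's own rules can take phase I past 12. With both escalations finished the total is 12 to 21 under the summary paragraph, or 18 to 24 under the six-patient MTD definition. A partly completed paediatric escalation can already reach 13.

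The phase II consequence is real but smaller. A ceiling of 22 holds only with at most three patients, across both age groups, at the non-final dose. It is at most 19 once both escalations finish, assuming the groups are pooled, which the plan does not say. Monitoring hardly changes: nothing in Table 2's stopping probabilities, and about five percentage points in Table 3 at true toxicity of 0.4 and 0.5.

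This should be corrected, but it does not undermine the design.

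**What to change.** 1. Reconcile Inclusion Criteria with Selection of Patients, Phase I, Phase II and the toxicity monitoring section, and with the SAP copy.
2. Restate the phase I maximum so that it counts both age groups within the 25, or state that 12 applies to one escalation only.
3. State the phase II maximum as 25 minus all patients treated at the non-final dose in either age group: 22 for one escalation, at most 19 when both finish. Add a note, or a short N = 19 companion to Table 3 using the figures above.
4. State whether the age groups are pooled for phase II efficacy and toxicity monitoring, and report them separately if their final doses differ.

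A separate item, which exists without any children, is how many patients must be treated at the final dose: the MTD definition and the toxicity section say six, while the summary paragraph does not require it.

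The cost is wording and at most one small table. No extra patients are needed and no stopping boundary changes.
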